5.2 Selection of Study Population

5.2.1 Inclusion Criteria

A subject will be eligible for study participation if he/she meets the following criteria:

1. The subject voluntarily signed the Independent Ethics Committee (IEC)/Institutional Review Board (IRB) approved Informed Consent form, prior to the conduct of any study procedures, or, where applicable (i.e., countries other than Germany*) for a given subject, the subject's legally authorized representative (LAR) signed the IEC/IRB approved Informed Consent form on behalf of the subject, prior to the conduct of any procedures. *For Germany, where the subject's LAR is not permitted to sign the IEC/IRB approved Informed Consent form on behalf of the subject, evaluation by an independent psychiatrist will be sought if the investigator who is evaluating the subject for inclusion in the study doubts the subject's cognitive ability to independently provide informed consent.
2. The subject completed the 52-week treatment period in Study M15-562.
3. In the opinion of the investigator, the subject was compliant during participation in Study M15-562.
4. The subject has an identified, reliable study partner (e.g., caregiver, family member, social worker, or friend), who has frequent contact with the subject (at least 10 hours per week) and who can accompany the subject to study visits to provide information regarding the subject's functional abilities.
5. If female, the subject must be either postmenopausal defined as:
 - age > 55 years with no menses for 12 or more months without an alternative medical cause

- age \leq 55 years with no menses for 12 or more months without an alternative medical cause AND a follicle-stimulating hormone (FSH) level of $>$ 40 IU/L.
OR
 - Permanently surgically sterile (bilateral oophorectomy, bilateral salpingectomy or hysterectomy).
OR
a woman of childbearing potential (WOCBP) practicing at least 1 protocol-specified method of birth control (refer to Section 5.2.4), starting on Study Day 1 through at least 20 weeks after the last dose of study drug.
6. If a male subject is sexually active, he must agree from Study Day 1 through at least 20 weeks after the last dose of study drug, to practice protocol specified contraception (refer to Section 5.2.4).
 7. Female subjects of childbearing potential must have a negative urine pregnancy test result on Day 1.

Rationale for the Inclusion Criteria

- | | |
|-------|--|

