5.2.2 Exclusion Criteria

A subject will not be eligible for study participation if he/she meets any of the following criteria:

1. The subject weighs less than 44 kg (97 lbs) at study entry.
2. The subject has any contraindication or inability to tolerate brain MRI (e.g., a pacemaker or any other implanted device or condition that would preclude proximity to a strong magnetic field).

3. The subject has any significant change in his/her medical condition that could interfere with the subject's participation in the study, could place the subject at increased risk, or could confound interpretation of study results. The Investigator must re-evaluate the subject for continuing participation and consider any factors including the interim development of any clinically significant neurological, hematological, autoimmune, endocrine, cardiovascular, neoplastic, renal, hepatic, metabolic, psychiatric, pulmonary, gastrointestinal, or other major disorder.
4. More than 8 weeks have elapsed since the subject received his/her last dose of study drug in Study M15-562.
5. The subject is concurrently enrolled in another interventional clinical study involving a therapeutic agent.
6. The subject is considered by the investigator, for any reason, to be an unsuitable candidate to receive ABBV-8E12 or the subject is considered by the investigator to be unable or unlikely to comply with the dosing schedule or study evaluations.
7. The subject is female and is pregnant, breastfeeding, or is considering becoming pregnant during the study or for approximately 20 weeks after the last dose of study drug.
8. The subject is male and is considering fathering a child or donating sperm during the study or for approximately 20 weeks after the last dose of study drug.

Rationale for Exclusion Criteria

- | | |
|-------------|---|
| 1, 2, 4 – 6 | To ensure the appropriate subject population |
| 3 | To ensure the safety of the subjects |
| 7, 8 | The effects of ABBV-8E12 on pregnancy are currently unknown |

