8.0 Statistical Methods and Determination of Sample Size

The data analysis will be grouped by assigned treatment sequences/group in Studies M15-562/M15-563: 2000/2000 mg, 4000/4000 mg, placebo/2000 mg, and placebo/4000 mg. If the treatment effect between each ABBV-8E12 dose and placebo is statistically significant at Week 52 in Study M15-562, the 2000/2000 mg and 4000/4000 mg groups could be combined as the early-start ABBV-8E12 treatment group, and the placebo/2000 mg and placebo/4000 mg groups could be combined as the delayed-start group for the delayed-start analysis. Details of the analyses will be specified in the statistical analysis plan (SAP).

Data Sets for Efficacy Analyses

Two data sets will be used for the efficacy analysis: an intent-to-treat (ITT) data set and a delayed-start data set.

ITT Data Set: The Study M15-563 ITT data set consists of all subjects who received any dose of study drug in Study M15-563. This is the primary efficacy analysis set for this

study. All efficacy analyses for Study M15-563 alone will be conducted on the ITT set unless otherwise specified.

Delayed-Start Data Set: The delayed start analysis data set includes efficacy data from both Studies M15-562 and M15-563. All subjects from Study M15-562 ITT data set will be included, regardless if they enroll in Study M15-563 or not. Subjects who complete Study M15-562 and rollover to Study M15-563 but have a gap of more than 8 weeks between study drug infusions before enrolling into Study M15-563 will be excluded from this analysis set.

Data Sets for Safety Analyses

The safety data sets will consist of all subjects who received any dose of study drug in Study M15-563. For the safety analyses, the actual treatment received will be used instead of the treatment assignment at the time of randomization. There are 2 safety datasets: a Stand-Alone safety data set and a cumulative safety data set as described below.

Stand-Alone Data Set: The stand-alone data set is the primary data set for the safety analysis, and will contain data from Study M15-563 only, regardless of the treatment received in Study M15-562. Baseline will be the last observation on or before the first dose of ABBV-8E12 in Study M15-563. If no Baseline is recorded in Study M15-563, the last value in Study M15-562 will be used as the Baseline.

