Cumulative Data Set: The cumulative data set will consist of data from both Study M15-562 and Study M15-563. It is the secondary data set for safety analyses. For subjects who were in the placebo group in Study M15-562, their safety data from Study M15-562 will not be included in the cumulative data sets but their safety data from Study M15-563 will be included. For Study M15-562 placebo subjects, Baseline will be the last observation prior to the first dose of study drug in Study M15-563. For subjects who were in ABBV-8E12 treatment groups in Study M15-562, Baseline for the safety analyses will be their Baseline in Study M15-562.

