5.0 Analysis Populations

5.1 Analysis Data Sets

Data Sets for Efficacy Analyses

Two data sets will be created for the efficacy analysis: an intent-to-treat (ITT) data set and a delayed-start data set.

ITT Data Set: the ITT data set consists of all subjects who received any dose of study drug in Study M15-563. All efficacy analyses will be conducted on the ITT data set using data from Study M15-563 alone unless otherwise specified.

Delayed-Start Data Set: The Delayed-Start data set includes all subjects from the Study M15-562 ITT data set who received placebo or ABBV-8E12 in Study M15-562 regardless of whether they enroll in Study M15-563 or not. For the Delayed-Start analysis, efficacy data for PSPRS total score from both Study M15-562 and Study M15-563 studies will be included.

Data Sets for Safety Analyses

The safety data set will consist of all subjects who received any dose of study drug infusion in Study M15-563. For safety analyses, the actual treatment received will be used instead of the treatment assignment at enrollment. There are two safety data sets: a Stand-Alone data set and a Cumulative data set.

Stand-Alone Data Set: The Stand-Alone data set is the primary data set for safety analyses, and will contain data from Study M15-563 only, regardless of the treatment received in Study M15-562. Baseline for the Stand-Alone data set will be the last observation on or before the first dose of ABBV-8E12 in Study M15-563. If no Baseline is recorded in Study M15-563, the last value in Study M15-562 will be used as the Baseline.

Cumulative Data Set: The Cumulative data set will consist of data from both Study M15-562 and Study M15-563. It is the secondary data set for safety analyses. For subjects who were in the placebo group in Study M15-562, their safety data from Study M15-562 will not be included in the Cumulative data set but their safety data from Study M15-563 will be included. For subjects who were in the placebo group in Study M15-562, Baseline will be the last observation prior to the first dose of study drug in Study M15-563. For subjects who were in ABBV-8E12 treatment groups in Study M15-562, Baseline for the Cumulative data set will be their Baseline in Study M15-562.

Data Sets for Biomarker Analyses

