10.2 Analysis of Adverse Events

The Stand-Alone data set will be the primary data set for adverse event summaries. Analyses that will also be performed on the Cumulative data set are as follows: adverse event overview, adverse event incidence by system organ class (SOC) and preferred term, adverse event incidence in descending frequency by overall subjects, and SAE incidence by SOC and preferred term.

All adverse events will be coded using the most current version of the Medical Dictionary for Regulatory Activities (MedDRA). A treatment-emergent adverse event (TEAE) is defined as any adverse event that begins or worsens in severity on or after the first study drug dose date and no more than 20 weeks after the last study drug dose date. Analysis of adverse events will also be conducted by geographical region (North America including US and Canada, European countries plus Australia, and Japan).

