10.2.1 Adverse Event Overview

The number and percentage of subjects experiencing one or more adverse events in the following adverse event categories will be summarized for each treatment group and overall subjects in both Stand-Alone data set and the Cumulative data set. No comparisons of treatment groups will be performed.

- Any TEAE
- Any TEAE that was rated reasonable possibility of being related to study drug by the investigator
- Any severe TEAE
- Any serious TEAE
- Any TEAE that led to discontinuation of study drug
- Any fatal TEAE
- All deaths

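### The Cumulative safety set holds only subjects who completed M15-562, so its added year can show no deaths and in effect no permanent stops (minor, cheap to fix)

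*SAP*

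**What the plan says.** Both documents restrict the safety population to subjects dosed in the extension. SAP 5.1: "The safety data set will consist of all subjects who received any dose of study drug infusion in Study M15-563". Protocol 8.0: "The safety data sets will consist of all subjects who received any dose of study drug in Study M15-563". The Stand-Alone set is primary and uses M15-563 data only. The Cumulative set is secondary and spans both studies: "The cumulative data set will consist of data from both Study M15-562 and Study M15-563" (Protocol 8.0). For subjects who had placebo in M15-562, "their safety data from Study M15-562 will not be included in the Cumulative data set" (SAP 5.1), so only the 2000/2000 mg and 4000/4000 mg columns gain the earlier year.

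Entry to M15-563 is conditional. Inclusion criterion 2 (Protocol 5.2.1) reads "The subject completed the 52-week treatment period in Study M15-562". Exclusion criterion 4 (Protocol 5.2.2) removes a subject if "More than 8 weeks have elapsed since the subject received his/her last dose of study drug in Study M15-562".

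SAP 10.2 lists the Cumulative outputs: "Analyses that will also be performed on the Cumulative data set are as follows: adverse event overview", then incidence by system organ class and preferred term, incidence by descending frequency, and serious adverse events. The overview rows in SAP 10.2.1 include TEAEs leading to discontinuation of study drug, fatal TEAEs and all deaths. Numbers and percentages of subjects "will be summarized for each treatment group and overall subjects in both Stand-Alone data set and the Cumulative data set". Exposure and subject-years (SAP 8.0) are prepared for the Stand-Alone set only.

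**The concern.** Long-term safety is a primary objective, and the Cumulative set is the only safety set that covers both studies. A table headed Cumulative, with a row for deaths and a row for discontinuations, invites the reader to take it as experience since first ABBV-8E12 dose. Under the set's definition it cannot be that for the early-start columns. The M15-562 active-arm subjects who died, stopped or did not roll over are in neither numerator nor denominator, and the subjects who are included passed that year free of terminal events as a condition of entry.

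There is a second, related difficulty. For adverse events that do not end participation, the early-start columns count about 52 more weeks than the delayed-start columns. The tables give percentages only, so a difference in follow-up could be read as a difference between treatment sequences.

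**Working it through.** **Step 1: what the definitions imply.** Both safety sets contain the same subjects, so their denominators agree.

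- *All deaths.* Nobody in the set died before the first M15-563 dose. The Cumulative row equals the Stand-Alone row in count and percentage.
- *Fatal TEAEs, and TEAEs leading to discontinuation.* These can exceed Stand-Alone only through an event that began in M15-562 and led to death or a stop in M15-563. SAP 10.2 counts an event as treatment-emergent only if it begins or worsens on or after first dose, so such an event may qualify on the Cumulative set and not on Stand-Alone.
- *Placebo/2000 mg and placebo/4000 mg columns.* Unaffected: these subjects' first ABBV-8E12 dose is in M15-563. The overall column mixes both kinds.

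**Step 2: possible size for terminal events, early-start columns.** The documents give no event, loss or rollover rates and state no figure to reproduce. As an illustration only, assume constant hazards that are equal in both studies: terminal-event risk p = 8% a year, so λ = −ln(0.92) = 0.0834; other loss in year 1 of q = 20%, so μ = −ln(0.80) = 0.2231; extension length T years.

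- Year-1 terminal events: y = λ/(λ+μ) × (1 − e^−(λ+μ)) = 0.272 × 0.264 = 7.18%.
- Rollover: r = 0.92 × 0.80 = 0.736.
- Percentage shown, S: with no other exits in the extension, 1 − 0.92^T; with the same 20% yearly loss continuing, 0.272 × (1 − 0.736^T).
- All exposed: A = y + r × S. Share of events omitted: y/A.
- Rate the present set would give, if one were computed: S/(1 + S/λ), against a true 8.3 per 100 subject-years.

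| Extension | Other exits in extension | Shown S | All exposed A | Share omitted | Rate on set ÷ true rate |
|---|---|---|---|---|---|
| 1 year | none | 8.0% | 13.1% | 55% | 49% |
| 1 year | 20% a year | 7.2% | 12.5% | 58% | 46% |
| 5 years | none | 34.1% | 32.3% | 22% | 80% |
| 5 years | 20% a year | 21.3% | 22.9% | 31% | 72% |

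The count is too low in every row. So is the hypothetical rate, because the added year brings time but no events. The percentage is too low at one year. At five years its direction changes with the assumption about exits during the extension.

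A separate check used different assumptions: 252 active subjects (two thirds of 378, an assumed split); year-1 deaths 3–10%; other stops 5–20%; completers not rolling over 0–10%; extension death hazard 0.05–0.20 a year; extension 0.5–5 years. Counts and rates were too low in all 36 scenarios, while the percentage was too low in some and too high in others.

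**Step 3: other adverse events, unequal follow-up.** Assume a 10% yearly risk in every group, no true difference and complete follow-up. Early-start columns show 1 − 0.9^(1+T); delayed-start columns show 1 − 0.9^T.

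| Extension | Early start | Delayed start |
|---|---|---|
| 1 year | 19.0% | 10.0% |
| 3 years | 34.4% | 27.1% |
| 5 years | 46.9% | 41.0% |

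The underlying rate is −ln(0.9) = 10.5 per 100 subject-years in both.

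**The case against.** The strongest reply is that nothing is hidden. Both documents say who is in the set, call it secondary, and state that the placebo year is excluded. Column labels such as 2000/2000 mg show that the subjects were dosed in both studies. The SAP follows Protocol 8.0 faithfully, and neither document presents the set as all exposed subjects. SAP 10.1 rules out comparisons between groups, and the primary Stand-Alone adverse event tables are untouched. A reader could also approximate Cumulative subject-years by adding about one year per early-start subject to the Stand-Alone figure.

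Most of this stands, and it is why the point is minor. It does not remove the problem, because the planned output still carries death and discontinuation rows on a set that cannot register those events in its added year, with no note saying so. Elsewhere the SAP takes the needed care: the Delayed-Start set in SAP 5.1 keeps M15-562 ITT subjects whether or not they enrolled in the extension, and SAP 12.1 reports biomarker times from first ABBV-8E12 dose and states the 52-week offset. The approximate subject-years would help with other adverse events but would leave the terminal-event rows incomplete.

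A reader might go further and infer that the plan will report a subject-year death rate that is too low. It will not: no such rate is planned on this set. Nor do the documents support saying that the planned percentages are always too low, since the direction turns on loss and rollover rates that they do not give.

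**Conclusion.** The point holds as a minor one. By construction, Cumulative terminal-event counts omit every death and permanent stop among M15-562 active-arm subjects who did not roll over. The all-deaths row adds nothing to Stand-Alone, and the fatal-TEAE and discontinuation rows can add only events that straddle the two studies. The percentage is conditional on completing M15-562. A terminal-event rate, if someone computed one on this set, would be too low. For other adverse events, the early-start and delayed-start columns are not comparable without exposure.

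The structural part rests on the set definitions and entry criteria alone. Every size given is an illustration under assumed constant hazards and should not be quoted as an expected result. It would also be wrong to infer that the omitted events go unreported: they belong to M15-562's own reporting. No test or primary safety table in M15-563 depends on this set.

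**What to change.** Define the Cumulative set as all subjects with at least one ABBV-8E12 dose in either study, counted from first ABBV-8E12 dose. Show the M15-562 active-arm subjects who did not roll over in two separate columns, *2000 mg, M15-562 only* and *4000 mg, M15-562 only*, and include them in the overall column. Add Cumulative subject-years and incidence per 100 subject-years beside the percentages in the adverse event overview, the system organ class and preferred term tables, and the serious adverse event tables. Make both changes together, since rates on the present rollover-only set would not cure the death row. Record the departure from Protocol 8.0 in the SAP.

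As a minimum, keep the set but label it *rollover subjects only, conditional on completing 52 weeks of M15-562*. Footnote the death, fatal-TEAE and discontinuation rows, and do not omit them: the last two can hold events that began in M15-562 and do not appear on Stand-Alone.

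The full fix needs SAP wording and data that the sponsor already holds. Its cost is pooling the M15-562 non-rollover records and producing and checking more tables. The minimum costs a label and a footnote.

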For the analysis of biomarker data, the actual treatment received will be used rather than the treatment assignment at enrollment. Descriptive statistics will be provided for all scheduled post-baseline times of measurement in Study M15-563, with all subjects who were administered a dose in Study M15-563 included. The descriptive statistics will also be provided for the baseline measurement. For subjects whose treatment in Study M15-562 was one of the ABBV-8E12 doses, the baseline value for Study M15-563 will be the baseline value of Study M15-562. For subjects whose treatment in Study M15-562 was placebo, the baseline value will be the last measurement obtained before the first dose of Study M15-563, which might be the last measurement of Study M15-562 as explained in Section 4.2.

Longer-Term Biomarker Data Set: Only data of subjects whose treatment in Study M15-562 was with one of the ABBV-8E12 dose levels will be included in this data set. The data set will include the data for all scheduled times of measurement of Study M15-563. The baseline value for this data set will be the baseline value of Study M15-562.

6.0 Demographics, Baseline Characteristics, Medical History, and Previous/Concomitant Medications

The data analysis will be conducted among treatment groups defined as Studies M15-562/M15-563: 2000/2000 mg, 4000/4000 mg, placebo/2000 mg, and placebo/4000 mg.

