10.3 Analysis of Laboratory Tests

Analyses of Laboratory tests will be performed on the Stand-Alone data set.

The laboratory tests are described in the following table.

Table 1. Laboratory tests

Hematology	Clinical Chemistry	Urinalysis
Hematocrit	Blood urea nitrogen (BUN)	Specific gravity
Hemoglobin	Creatinine	pH
Red blood cell (RBC) count	Total bilirubin	
White blood cell (WBC) count	Albumin	
Neutrophils	Aspartate aminotransferase (AST)	
Bands (if detected)	Alanine aminotransferase (ALT)	
Lymphocytes	Alkaline phosphatase	
Monocytes	Sodium	
Basophils (if detected)	Potassium	
Eosinophils (if detected)	Calcium	
Platelet count (estimate not acceptable)	Inorganic phosphate	
Mean corpuscular volume (MCV)	Uric acid	
Mean corpuscular hemoglobin concentration (MCHC)	Cholesterol	
Prothrombin time (PT)	Total protein	
Activated partial thromboplastin time (aPTT)	Glucose	
PT/INR (Prothrombin Time/International Normalized Ratio)	Triglycerides	
	Bicarbonate/Carbon Dioxide (CO ₂) Chloride	

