10.3.3 Potentially Clinically Significant Laboratory Values

Criteria for potentially clinically significant (PCS) values have been predefined for selected laboratory variables as outlined in [Appendix A](#). For each variable, a summary of the number and percentage of subjects in each treatment group who have at least one double-blind observation that meets the PCS criteria and is more extreme than their baseline value will be provided. A listing will also be prepared that will include, for each variable, all observations for each subject that met the PCS criteria for that variable at any time during the study.

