10.4 Analysis of Vital Signs and Weight

Vital sign and weight data analyses will be performed on Stand-Alone data set. Vital sign variables include: diastolic blood pressure, systolic blood pressure and pulse rate at

supine and standing positions, orthostatic diastolic blood pressure, orthostatic systolic blood pressure, orthostatic pulse rate, and body temperature. The calculations of orthostatic vital sign values are:

- Orthostatic SBP (mmHg) = Standing SBP – Supine SBP
- Orthostatic DBP (mmHg) = Standing DBP – Supine DBP
- Orthostatic Pulse Rate (bpm) = Standing Pulse Rate – Supine Pulse Rate.

Weight variables include weight and BMI.

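### For the early-start groups, every laboratory, vital-sign, weight and ECG change is measured from an on-drug baseline, so the extension tabulates no change since before ABBV-8E12 in its longest-exposed subjects

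*SAP*

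**What the plan says.** **Stand-Alone set (primary for safety, SAP 5.1).** It "will contain data from Study M15-563 only, regardless of the treatment received in Study M15-562". Its baseline rule is the same for all four sequences: "Baseline for the Stand-Alone data set will be the last observation on or before the first dose of ABBV-8E12 in Study M15-563". If M15-563 has no baseline value, the last M15-562 value is used.

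**Where the measured safety variables go.** SAP 10.3: "Analyses of Laboratory tests will be performed on the Stand-Alone data set". SAP 10.4: "Vital sign and weight data analyses will be performed on Stand-Alone data set". SAP 10.5 says the same for ECG. The outputs are mean changes, laboratory shift tables and counts of potentially clinically significant (PCS) values. A subject enters a PCS count only with an observation that "meets the PCS criteria and is more extreme than their baseline value". A separate listing shows all observations meeting the criteria at any time in the study (SAP 10.3.3, 10.4.2, 10.5.2). SAP Appendices B and C define several limits wholly or partly as change from baseline: weight 7%, QTcF more than 60 msec, blood pressure, pulse and temperature.

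**Cumulative set (secondary).** For subjects on ABBV-8E12 in M15-562, "Baseline for the Cumulative data set will be their Baseline in Study M15-562". Its use is given in SAP 10.2: "Analyses that will also be performed on the Cumulative data set are as follows: adverse event overview", followed by adverse event incidence and serious adverse event incidence. Protocol 8.1.2.2 has the same list. Neither document assigns a laboratory, vital-sign, weight or ECG analysis to it.

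**Biomarkers.** For early-start subjects, SAP 5.1 goes back to the parent study: "the baseline value for Study M15-563 will be the baseline value of Study M15-562". SAP 12.1 also reports time from the first ABBV-8E12 dose.

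**Comparisons.** SAP 10.1 makes none between groups for safety. Protocol 8.1.2 had planned ANOVA on change from baseline.

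**The concern.** Long-term safety is a primary objective. In two of the four columns, change from baseline starts before any drug. In the other two it starts after a year of it. The subjects with the longest exposure therefore have no tabulated laboratory, weight, vital-sign or ECG change since before drug, and limits defined as a change restart at zero on entry to the extension. Slow cumulative change is something a long-term extension is well placed to detect, yet a change split across the two studies can stay below the limit in each.

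This looks more like an omission than a choice. SAP 5.1 writes out a pre-drug baseline for early-start subjects in the Cumulative set, but the only tables run on that set are adverse event tables. Treatment-emergent events are defined by dose dates (SAP 10.2), so those tables need no baseline value.

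**Working it through.** The plan states no figure here to reproduce. The check traces the baselines and then illustrates the consequence.

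**1. Baseline by sequence (SAP 4.2, 5.1)**

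| Sequence | Stand-Alone baseline | Cumulative baseline |
|---|---|---|
| placebo/2000, placebo/4000 | before any ABBV-8E12 | essentially the same value |
| 2000/2000, 4000/4000 | after about 52 weeks on drug | before any ABBV-8E12 |

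The fallback to the last M15-562 value does not help early-start subjects, because that value is also on drug.

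**2. Is the early-start baseline washed out?** Inputs: half-life 27 to 37 days (Protocol 3.0, single-dose study); 28-day dosing; the 45-day rule (Protocol 5.1); the 8-week limit (exclusion criterion 4). Assuming simple exponential decay, the fraction remaining is 2^(−days/half-life):
- 28 days: 49% to 59%
- 45 days: 32% to 43%
- 56 days: 24% to 35%

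It is an on-drug value even at the longest permitted gap.

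**3. Change split across the studies, against the SAP's own limits (hypothetical subjects)**
- Weight: 5% lost in each study. Total 1 − 0.95 × 0.95 = 9.75%, over 7%; from the M15-563 baseline it is 5%, not flagged.
- QTcF: +40 msec, then +25 msec. Total 65 msec, over 60; from the M15-563 baseline it is 25, not flagged.

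Neither study flags these subjects if M15-562 uses similar limits, which is an assumption because its SAP is not supplied.

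**4. How far the choice of baseline could move a count.** Assume annual weight change is normal with mean m and SD s (in %), independent and additive between years. At M15-563 Week 52, the share meeting the 7% loss limit is Φ((−7 − m)/s) from the M15-563 baseline and Φ((−7 − 2m)/(s√2)) from the M15-562 baseline.

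| m, s | M15-563 baseline | M15-562 baseline |
|---|---|---|
| −2, 3 | 4.8% | 24.0% |
| −2, 5 | 15.9% | 33.6% |
| −4, 3 | 15.9% | 59.3% |
| −4, 5 | 27.4% | 55.6% |

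These rates are assumed, not document figures. The gap reflects a second year of change from any cause and is not a drug effect.

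**5. Side-by-side reading.** A lasting drug effect of size d, fully reached within the first year, shows as d in the placebo-start columns and as 0 in the early-start columns.

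**6. Subjects affected.** 378 were randomised in M15-562 (SAP 4.3). Assume two-thirds were on active drug; the superseded target in Protocol Appendix E, 220 on drug and 110 on placebo, has that ratio. With rollover fraction r the number is 378 × 2/3 × r: 252 at r = 1, or 126 at an assumed r = 0.5.

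**The case against.** The other side has substance, and it rules out several stronger readings.

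- **A reader might infer that first-year drug effects are hidden.** The documents do not support that. For early-start subjects that year is the treatment period of placebo-controlled M15-562, and M15-563 shows first-year change directly in the placebo-start groups. The effects are not re-tabulated here, which is a smaller matter.
- **A reader might infer that an abnormality carried over from M15-562 is never counted.** A carried-over ALT above 3 × ULN still appears in the listing, and it is counted if any later reading exceeds baseline. If baseline and n later readings are treated as exchangeable, the chance that baseline is the highest is 1/(n + 1): 25% with the three Year 1 laboratory visits, 12.5% with all seven. So 75% to 87.5% would be counted. That is generous, because choosing subjects already abnormal at baseline makes baseline more likely to be the highest. The listing does not rescue limits defined as change, because no other baseline is specified for it.
- **A reader might infer that the pre-drug baseline is used nowhere.** It goes unused only for early-start subjects. For placebo-start subjects it drives every table.
- **A reader might infer invalid group tests.** SAP 10.1 makes no comparisons, so no p-value is affected. The Protocol 8.1.2 ANOVA would have carried the mismatch.
- **Adverse events give partial cover.** Protocol 5.3.1.1.10 requires a PCS laboratory value to be reported as an adverse event or the reason documented, and the Cumulative tables include early-start events from M15-562.
- **The choice is prespecified.** Protocol 8.0 makes Stand-Alone primary. That supports keeping it, but does not explain defining a second baseline and leaving it unused.

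What stands is that no planned M15-563 table gives change from before drug in early-start subjects, and neither the listings nor the adverse event tables recover a change split across the two studies.

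**Conclusion.** The point holds as a gap in the planned safety output. For the 2000/2000 mg and 4000/4000 mg groups, mean changes, shifts, PCS counts and change-based limits all run from a value taken after about a year on ABBV-8E12. In the placebo-start columns the same labels mean change from a drug-naive value. The loss is greatest for limits defined as change (weight, QTcF, blood pressure, pulse, temperature) and smallest for absolute laboratory limits, which the listings still show.

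At most 252 subjects are affected, under the two-thirds and full-rollover assumptions. The weight and QTcF cases show what the rules allow and are not expected frequencies. The statement that split change is flagged in neither study also assumes similar limits in M15-562. Nothing here invalidates the Stand-Alone tables. They answer a narrower question than the long-term safety objective asks, and their columns should not be read across sequences as if exposure were equal.

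**What to change.** Keep the Stand-Alone tables as primary. In SAP 10.3, 10.4 and 10.5, add supplementary mean-change, laboratory shift and PCS summaries on the Cumulative set:

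- Use the baseline already written in SAP 5.1: the M15-562 Baseline for early-start subjects, and the last value before the first M15-563 dose for placebo-start subjects.
- Apply the test for being more extreme than baseline, and the change-based limits in SAP Appendices B and C, to that baseline.
- Index visits by time since first ABBV-8E12 dose, as SAP 12.1 does for biomarkers, so that columns are read at equal exposure.

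The cost is SAP wording and programming; no new data collection is needed. Three downsides belong in the SAP text and table footnotes:

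- There is more output.
- The Cumulative set is restricted to subjects dosed in M15-563, so early-start subjects who left during or after M15-562 are absent.
- Early-start subjects have up to one more year of observation without concurrent placebo, because placebo subjects' M15-562 data are excluded from the set. Ever-PCS counts and minimum or maximum values must therefore not be compared across sequences without matching exposure time. Even when matched, they cannot separate drug effect from disease progression.
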